# 9.3.3 Vaccination procedures

The following procedures will be performed at Visit 1 (Day 1) and Visit 5 (Day 22):

- 1. Check contraindications to vaccination and criteria for encountering toxicities of vaccination (see Sections 7.2 and 7.3).
- 2. Prepare the investigational vaccine/placebo according to the Pharmacy Manual (see Section 8.2)
- 3. Inject the investigational vaccine or placebo (see Section 8.2).

# 9.3.4 Post-vaccination procedures

The following post-vaccination procedures will be performed at Visit 1 (Day 1) and Visit 5 (Day 22):

- 1. After vaccination, the subject will be observed for at least 6 hours on site, including observation for immediate reactions and body temperature measurement. Vital signs will be performed at 1, 3, and 6 h (±15 min) post each immunization. Information should be recorded in the eCRF as immediate reactions. The investigator or delegate will take the opportunity to remind the subject how to measure solicited reactions and body temperature as part of this observation period. All safety data will be collected in the subject's source documents.
- 2. Provide the subject with a diary card, and train the subject on how to use it.
  - Careful training of the subject on how to record concomitant medications, how to measure solicited reactions and body temperature, how to complete the diary card and how often to complete the diary card. Training should be directed at the individual(s) who will perform the measurements of solicited reactions and those who will enter the information into the diary

card. This individual may or may not be the subject, but if a person other than the subject enters information into the diary card, this person's identity must be documented in the trial file and this person must receive training on the diary card. Training of the subject on how to measure a vaccination site AE should be performed while the subject is under observation after vaccination.

Diary card instructions must include the following: the subject must understand that timely completion of the diary card on a daily basis is a critical component of trial participation. The subject should also be instructed to write clearly and to complete the diary card with sign pen. Any corrections to the diary card that are performed by the person completing the diary card should include a single strikethrough line with a brief explanation for any change and be primeed and dated.

# Please note:

Diary cards will be the only source document allowed for remote collection of solicited local and systemic reactions (including body temperature measurements). The following additional rules apply to the documentation of safety information collected by diary card:

- o Diary cards should be reviewed with the subject.
- No corrections or additions to the diary card will be allowed after it is reviewed with the investigator/designee.
- O Any data that are identified as implausible or incorrect, and confirmed by the subject to be a recording error should be corrected by the subject on the diary card (the correction should include a single strikethrough line and should be primeed and dated by the subject).
- Any blank or illegible fields on the diary card not otherwise corrected as above will be missing in the eCRF.
- The study site should enter all readable entries on the diary card into the eCRF.
- O Any newly described solicited safety information should be added to the diary card by the subject and primeed and dated. Any new unsolicited safety information would be recorded in the subject source document as a verbally reported event and therefore captured as an AE and recorded in the AE eCRF.
- Starting on the day of vaccine/placebo administration, the subject will check for specific types of events at the vaccination site (solicited local reactions), any specific generalized symptoms (solicited systemic reactions), body temperature (axillary), any other symptoms or change in the subject's health status, and any medications taken. These solicited reactions and body temperature will be recorded in the diary. Assessments should preferably take place in the evening at day's end using the same method of measurement every day.
- Temperature measurement is to be performed using the thermometer provided by the study site. If the subject feels unusually hot or cold during the day, the subject should

- check his/her temperature. The highest body temperature measured that day should be recorded on the diary card.
- The measurement of solicited local reactions (pain/tenderness, erythema/redness, and induration/swelling) is to be performed using the ruler provided by the study site. If multiple measurements are taken during the day, the highest measured value should be recorded on the diary card.
- O The collection on the diary card of body temperature, solicited local reactions, and solicited systemic reactions will continue for a total of 14 days following each vaccine/placebo administration. The collection on the diary card of unsolicited AEs and medications will continue for 21 days following prime vaccination and 28 days following boost vaccination.
- The healthcare professional reviewing the data on the diary cards will discuss the AEs (if any) reported by the subject and will determine if any additional diagnoses and/or AEs are present and/or concomitant medications have been used.
- 3. At Visit 5 (Day 22), review the previous diary card with the subject and collect it.
- 4. Provide contraception guidance (see Section 9.1.8).
- 5. Provide the subject with a written reminder of the next planned trial activity. The subject will be reminded to complete the diary card daily and to contact the study site if there are any questions and to contact the site immediately (or as soon as the subject is medically stable) if the subject has a medical condition that leads to a hospitalization or an emergency room visit or is otherwise perceived as serious. Available contact details will be provided to the subjects.
- 6. Schedule the next site visit with the subjects.

#### 9.3.5 Main visits post vaccination

The following main visits post vaccination will be performed:

- 1. Collect travel history (to SARS-CoV-2 endemic countries and SARS-CoV-2 endemic regions of China) and concomitant medications/vaccinations (see Section 9.1.2).
- 2. Perform symptom-directed physical examination (if deemed necessary, see Section 9.1.4).
- 3. Check vital signs (see Section 9.1.5).
- 4. Collect blood samples for routine safety laboratory testing, immunogenicity assessment and CMI testing (see Section 9.1.6).
- 5. Collect urine sample for routine safety laboratory testing (urinalysis; see Section 9.1.6).
- 6. Review the previous diary card with the subject and collect it (see Section 9.3.4).
- 7. Provide the subject with a new diary card, and remind the subject on how to use it (see Section 9.3.4).
- 8. Provide contraception guidance (see Section 9.1.8).

- 9. Provide the subject with a written reminder of the next planned trial activity. The subject will be reminded to complete the diary card daily. The subject will be reminded to contact the site if there are any questions and to contact the site immediately (or as soon as the subject is medically stable) if the subject has a medical condition that leads to a hospitalization or an emergency room visit or is otherwise perceived as serious. All contact details will be provided to the subject.
- 10. Schedule the next site visit with the subjects.

# 9.3.6 Follow-up extension

The extension visits will be performed at Visit 10 (Month 3), Visit 11 (Month 6), and at Month 12 (Visit 12). If a subject terminates earlier, a final Visit procedure should be performed, if possible.

The following procedures will be performed:

- 1. Collect travel history (to SARS-CoV-2 endemic countries and SARS-CoV-2 endemic regions of China) and concomitant medications/vaccinations (see Section 9.1.2).
- 2. Perform symptom-directed physical examination (if deemed necessary, see Section 9.1.4).
- 3. Check vital signs (see Section 9.1.5).
- 4. Collect blood sample for immunogenicity assessment (see Section 9.1.6.5).

# 9.4 Biological sample retention and destruction

In this trial, specimens for testing will be collected as described in Section 9.1.6. After blood draw and serum processing, the serum samples will be preserved and retained as required by applicable laws. The Fosun Phar. has put into place a system to protect the subjects' personal information to ensure optimal confidentiality and defined standard processes for sample and data collection, storage, analysis, and destruction.

#### 10.0 ADVERSE EVENTS

#### 10.1 Definitions

#### 10.1.1 Adverse events (AEs)

Adverse Event (AE): refers to any adverse medical event that occurs in patients or subjects in drug clinical study. It does not necessarily have a causal relationship with drug treatment. An adverse event can be an unfavorable sign, symptom or disease that is not related to the purpose of the medication (including abnormal laboratory tests, etc.), in spite of the causal relationship with the drug.

It includes any new occurrence or deterioration in severity or frequency compared to baseline conditions, including abnormal results of laboratory tests (with clinical manifestations).

#### AE excludes:

- Medical or surgical procedures, such as operation, endoscopy, tooth extraction, infusion (the
  operation should not be collected as AE, but the diseases leading to these operations should
  be reported as AE);
- Existing diseases or conditions that exist or have been detected but have not worsened prior to the start of using the study drug, including abnormal results of laboratory tests.
- Transitory effects on laboratory tests due to the known mechanism of action of the drug, where there is no manifest clinical risk or evidence of potential lasting harm, judged by the investigator.

Treatment-emergent AE (TEAE) is defined as any AE with an onset date on or after the first administration of IMP (if the AE was absent before the first vaccination of IMP) or worsened after the first vaccination of IMP (if the AE was present before the first administration of IMP). AEs with an onset date more than 28 d after the last vaccination of IMP will be considered as treatment emergent only if assessed as related to IMP by the investigator.

#### 10.1.2 Solicited reactions

The occurrence of selected indicators of safety will be measured/collected for 14 days after each vaccination (including the days of vaccine vaccination), see details in following **Table** 5.

Table 4 Solicited local and systemic reactions

Local reactions (vaccination site):	Pain/tenderness
	Erythema/redness
	Induration/swelling
Systemic reactions:	Fever (a)
	Nausea
	Vomiting
	Diarrhea

Headache
Fatigue
Myalgia
Arthralgia
Chills
Loss of appetite
Malaise

(a) Based on recorded body temperature, fever is defined as axillary temperature ≥37.3°C.

The intensity of solicited safety parameters will be assessed respectively as described in grading scale of Appendix B and C.

Solicitation adverse reactions: there is at least a reasonable possibility of a causal relationship between vaccines and adverse events, that is, causality cannot be ruled out.

# 10.1.3 Serious adverse events (SAEs)

Serious Adverse Event (SAE): Serious adverse event is defined as any untoward medical occurrence that (at any dose):

- Results in death
- Is life-threatening

(It refers to an event in which the patient is at risk of death at the time of the event; it does not refer to an event which hypothetically may have caused death if it is more severe.)

• Requires hospitalization or prolongation of existing hospitalization

**Note:** In general, hospitalization is defined that the patient stays in the hospital or emergency ward for observation (usually stays for one night at least) and/or receives the treatment which is not suitable to be given in doctor's office or outpatient department. Complications that occur during hospitalization are also considered as AE. If a complication prolongs hospitalization or meets any other criteria of serious event, the event is serious. When it is uncertain whether it is hospitalization or whether hospitalization is needed, the event should also be considered serious. Hospitalization required by selective treatment or due to original disease which does not get worse since baseline does not belong to AE.

• Results in persistent or significant disability/incapacity

**Note:** Disability is defined that the person's ability to do activity of normal life is significantly influenced. It does not include events with little clinical significance, such as simple headache, nausea, vomiting, diarrhea, flu or accidental trauma (such as ankle sprain). These events may influence daily life function, but they will not result in obvious loss of function.

- Caused a congenital anomaly/birth defect of offspring
- Other significant medical events

Other significant medical events: In some cases, medical and scientific judgment should be made to decide whether expedited report is needed. If the significant events do not immediately threaten life, cause death or require hospitalization, but medical measures are needed to prevent the above situation, then these event are also considered serious.

Note: The following hospitalization treatments are not considered as serious adverse events, since there are no adverse events related to hospitalization (i.e, there are no adverse medical events).

- Temporary care and hospitalization
- Hospitalization due to social reason, for example, hospital admission for convenient care.
- Scheduled hospitalization according to the study protocol, for example, hospitalization for administration of the study vaccine or insertion of study vaccine or laboratory test required by protocol.
- Scheduled hospitalization, selective operation or examination which the patient plans to undertake for pre-existing disease prior to the informed consent (in this case, the disease that requires hospitalization does not get worse or develop into a new disease after the administration of study vacccine, which should be also proved by the original document).
- Hospitalization for daily maintenance of equipment which have been in place before study (such as battery replacement).

Any confirmed cases of COVID-19 disease that occur during observation should be reported as SAE, where the intensity of the corresponding AE is rated as "moderate" or "severe" (according to the criteria provided in appendix B and appendix C), and necessary isolation or hospitalization should be performed in accordance with the Diagnosis and Treatment Protocol for Novel Coronavirus Pneumonia (Trial Version 7). If no other SAE definition is deemed appropriate, then "other significant medical events" should be used as the SAE criterion.SAE forms should be completed, including follow-up information, as detailed in section 10.2.3, for the preparation and distribution of SAE reports and notes.

# 10.1.4 Adverse events of special interest

Enhanced respiratory disease or flu-like symptomatology not-resolved after 7 d or with symptom kinetics that are inconsistent with a relationship to RNA immunization, judged by the investigtors, will be considered adverse events of special interest (AESI).

All AESI, whether or not serious adverse events, whether or not have causal relationship with the investigational product, need to inform Beijing Fosun medicine science and technology development co., LTD. (the Fosun) within 24 hours, and fill out the form of serious adverse events and send to the pharmacovigilance department. If the adverse events of special interest meet the SAE standard, it needs to be handled and reported according to the SAE.

#### 10.1.5 AE associated with an overdose or error in vacccine administration

If the subject presents with symptoms due to overdose or error in vacccine administration, the vacccine administration of overdose and error and all related symptoms should be recorded on AE page of eCRF and should be reported to the Fosun according to the SAE procedure. The overdose which does not cause any symptoms should also be immediately reported within 24 hours. If there are serious consequences or the subject presents with symptoms which meet the assessment criteria of SAE after overdose, this overdose should be reported as SAE.

# 10.2 Collection and record of safety events

# 10.2.1 Collection and reporting of solicited reactions

The occurrence of selected symptoms indicative of safety will be collected on diary cards by the subjects for 14 days following each investigational vaccine/placebo administration (i.e, the day of vaccination +13 subsequent days) and will be recorded on the "Local and Systemic reactions" eCRF (if applicable). These will be summarized in the final report under the category "solicited reactions" to differentiate them from unsolicited AE. Any solicited local or systemic reaction observed beyond 14 days after vaccination will be recorded as unsolicited AE on the Adverse Event eCRF. Any solicited continuing local (vaccination site) or systemic reactions observed beyond 14 days following each trial vaccination will be additionally recorded on the Adverse Event eCRF for follow-up. For these persistent/prolonged solicited reactions, the end date will be captured on the Adverse Event eCRF to permit a separate analysis from the unsolicited AE.

#### 10.2.2 Collection and reporting of unsolicited AEs

Unsolicited AE occurring within 21 days after the prime vaccination and within 28 days after boost vaccination of vaccine/placebo will be collected on diary card (ie, day 22 to day 50 of the trial). AEs leading to withdrawal or discontinuation will be collected throughout the trial. Investigators should report collections of signs and symptoms as diagnosis AEs e.g. 'flu-like symptoms' or 'injection site reaction'.

Related AE/SAE occurring after 28 days after boost vaccination should also be collected and reported.

The following information will be documented for each event:

- Reported term for the Adverse Event,
- Start and end date,
- Serious (Y/N),
- Severity should be judged clinically by the investigator according to the grading standard in 10.3.1. For reference to the specific events listed in Appendix B and Appendix C, refer to the grading standards of the corresponding guidelines.
- Investigator's opinion on the causality (relationship) between the event and administration of trial vaccine(s),

- Investigator's opinion of the causality (relationship) to trial procedure(s), including the details of the suspected procedure,
- Actions taken,
- Outcome of event.

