Blood samples of subjects in elderly group will be collected at the following site visit for different tests: at Screening Visit (Visit 0) for eligibility screening tests (including clinical laboratory), at Visits 2, 3, 6 for regular safety laboratory testing, at Visit 1 (prior to prime vaccination) and Visit 5 (prior to boost vaccination), 6, 8, 11, 12 for humoral immunity (antibody). Blood sample will be collected at Visit 1 (prior to prime vaccination) and Visit 6 for cell-mediated immunity (CMI). Urine samples will be collected at Screening Visit (Visit 0) for eligibility screening and collected at Visits 2, 3, 6 for regular safety laboratory testing; serum samples of women

of childbearing potential will be collected at Screening Visits (Visit 0) and Visit 5 for pregnancy test. Fingertip blood will be collected during the screening visit (visit 0) for detection of SARS-CoV-2 antibody and HIV antibody.

Each subject will receive diary cards to collect solicited reaction for 14 days after each vaccination (including the days of vaccine/placebo vaccination), and unsolicited AE for 21 days after prime vaccination and 28 days after boost vaccination (including the days of vaccine/placebo vaccination). Additional safety assessments will include vaccine related adverse events (AEs) collection for the rest of the entire trial.

[figure not shown]

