## **5.2.2** Secondary endpoints

Safety and tolerability of BNT162b1, as determined by:

- The proportion of subjects experiencing SAEs, occurring up to Day 21 after prime vaccination and Day 28 after boost vaccination, up to Month 3, 6 and 12.
- The proportion of subjects experiencing AE associated with BNT162b1, occurring up to Month 3, 6 and 12.
- The proportion of of subjects experiencing abnormal markers of hematology, blood chemistry and urine analysis, occurring at Hour 24 and Day 7 after prime vaccination and Day 7 period after boost dose of BNT162b1 or placebo.

*Immunogenicity of BNT162b1, as determined by:* 

- Geometric mean titer (GMT) of anti-S1 IgG antibody at Day 7, Day 21 after prime vaccination, at Day 7, Day 21 after boost vaccination, and at Month 3, 6 and 12.
- Geometric mean titer (GMT) of anti-RBD IgG antibody at Day 7, Day 21 after prime vaccination, at Day 7, Day 21 after boost vaccination, and at Month 3, 6 and 12.
- GMT of SARS-CoV-2 neutralizing antibody (including true virus-based SARS-CoV-2 neutralizing test) at Day 7, Day 21 after prime vaccination, at Day 7, Day 21 after boost vaccination, and at Month 3, 6 and 12.
- Fold increase in antibody anti-S1 IgG antibody titers, as compared to baseline, at Day 7, Day 21 after prime vaccination, at Day 7, Day 21 after boost vaccination, and at Month 3, 6 and 12.
- Fold increase in antibody anti-RBD IgG antibody titers, as compared to baseline, at Day 7, Day 21 after prime vaccination, at Day 7, Day 21 after boost vaccination, and at Month 3, 6 and 12.
- Fold increase in SARS-CoV-2 neutralizing antibody titers (virus neutralizing test), as compared to baseline, at Day 7, Day 21 after prime vaccination, at Day 7, Day 21 after boost vaccination, and at Month 3, 6 and 12.
- Seroconversion rates (SCR) defined as a minimum of 4-fold increase of antibody titers, as compared to baseline, at Day 7, Day 21 after prime vaccination, and at Day 7, Day 21 after boost vaccination.

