# 10.2.3 Collection and reporting of SAEs

For any SAE during the trial, the investigator should actively take appropriate action to ensure the safety of subject, no matter whether the SAE is related to study vacccine. The investigator should report to Fosun whthin 24 hours of being informed of the SAE.

For reports of deaths, the investigator shall provide the Fosun and the ethics committee with other information as required, such as an autopsy report and a final medical report.

The investigator shall sign and read the clinical trial safety information provided by the sponsor in a timely manner, and shall consider the treatment of the subject, whether to adjust accordingly, communicate with the subject as soon as necessary, and report to the ethics committee the suspicious and unexpected serious adverse reactions (SUSAR) provided by the sponsor.

The investigator shall follow up the SAE according to the protocol requirements, and provide a detailed, written follow-up report within 24 hours after receiving the follow-up information, in the same manner as above.

The sponsor or its representative shall evaluate and report the SAE (including SUSAR) in the clinical trial in accordance with the latest applicable regulatory requirements for the clinical trial of the investigational product.

Contacts of serious adverse event reports:

Table 5 Contact information for serious adverse events reporting

Unit	Phone	Reporting way
Pharmacovigilance Department of Beijing Fosun		Email: [contact]
Jiangsu Center for Disease Control and Prevention		

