- > TEAEs leading to discontinuation by SOC and PT
- Related TEAEs leading to discontinuation by SOC and PT
- Unrelated TEAEs leading to discontinuation by SOC and PT
- ➢ AESIs by SOC and PT
- Related AESIs by SOC and PT
- Unrelated AESIs by SOC and PT
- ➢ TESAEs by SOC and PT
- Related TESAEs by SOC and PT
- > Unrelated TESAEs by SOC and PT

The DLT AE and related DLT AE will be summaried by group. The distribution of severity, injection stage, occurrence will be provided for TEAEs and related TEAEs. The episodes of AEs, number and percentage of subjects with TEAEs will be summarized by worst grade by PT nested within SOC.

For each solicited reaction (including fever), the number and percentage of subjects with TEAEs within 14 days after each immunization will be summarized by severity and overall.

TEAE after each immunization will be summarized based on Safety Set for prime and boost immunization, respectively.

The following TEAEs will be listed by subject: related TEAEs, unrelated TEAEs, TEAEs leading to discontinuation, AESIs and SAEs.

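### The documents contradict each other on whether unrelated SAEs starting more than 28 days after the boost are collected and counted

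*Protocol*

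**What the plan says.** **Endpoint.** Protocol 5.2.2 (and the synopsis) lists "The proportion of subjects experiencing SAEs, occurring up to Day 21 after prime vaccination and Day 28 after boost vaccination", and then up to Months 3, 6 and 12. No causality qualifier is attached. The next bullet, on AEs to the same horizons, is expressly limited to those associated with the vaccine, so the contrast looks deliberate.

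**Provisions that point to related events after 28 days post boost**
- Protocol 10.2.2: "Related AE/SAE occurring after 28 days after boost vaccination should also be collected and reported". The exception there that does not depend on causality is "AEs leading to withdrawal or discontinuation will be collected throughout the trial".
- Synopsis, vaccination protocol and visit schedule: "Additional safety assessments will include vaccine related adverse events (AEs) collection for the rest of the entire trial". SAEs are not mentioned.
- Protocol 13.1.4 refers to vaccine-related AEs for the period after 28 days.
- Protocol 10.1.1: "AEs with an onset date more than 28 d after the last vaccination of IMP will be considered as treatment emergent only if" the investigator assesses them as related.
- Protocol 9.3.6 lists the procedures for the Month 3, 6 and 12 visits and has no AE or SAE item.

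**Provisions that point to all SAEs**
- Protocol 10.2.3 covers any SAE during the trial, related or not: "The investigator should report to Fosun whthin 24 hours of being informed of the SAE". No end date is given.
- Table 2 marks AE recording at Visits 10, 11 and 12 in both age groups, without a causality filter.
- Protocol 13.1.4 lists any SAE separately from related SAEs.
- SAP 7.1.2 and 7.6.1 count an AE on or after the first immunization as a TEAE, with no 28-day cut and no relatedness test.
- SAP 7.6.1 plans "TESAEs by SOC and PT", followed by related and unrelated TESAEs separately.

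SAP 2.3 states that its analyses are consistent with the protocol.

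**The concern.** The endpoint needs every SAE to Month 12. A site that follows 10.2.2 as worded could record only the SAEs it judges related after 28 days post boost. A site that follows 10.2.3 would record all of them. No provision says which section prevails, so both sites could claim to be following the protocol. An SAE that is never recorded cannot be restored at analysis.

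The analysis side has a parallel problem. An analyst using the protocol's TEAE definition would drop unrelated late SAEs from a treatment-emergent table, and an analyst using the SAP's definition would keep them. The SAP does not declare the difference.

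Causality is a weak filter for late events. Under Protocol 10.3.2, a distant time relation to dosing points towards possibly unrelated, and that category is not counted as related. An SAE many months after the last dose therefore tends towards unrelated by the wording of the scale. Some of these judgements may also be made with allocation known. Protocol 8.5 opens the blind at the analysis 28 days after the boost and promises continued blinding only for subjects, whereas 8.3 says that researchers and sponsor study management stay blinded throughout.

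**Working it through.** **1. The plan's own figure.** Protocol 13.3 and SAP 4.3 give 86.5% as the probability of at least one TEAE in 24 subjects at a rate of 8%. Check: 1 − (1 − 0.08)^24 = 1 − 0.92^24 = 0.8648. It reproduces. It has no direct bearing here, because the documents state no SAE rate.

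**2. One event traced through the provisions.** Take an SAE with onset at Month 8 that the investigator judges unrelated and that does not lead to withdrawal.

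| Question | Provision | Answer |
|---|---|---|
| Does it belong to the endpoint? | Protocol 5.2.2 | Yes |
| Is it collected? | Protocol 10.2.2, narrow reading | Not named |
| Is it collected? | Protocol 10.2.3 | Yes, within 24 hours |
| Is it collected? | Table 2, Visit 12 | Yes |
| Is it treatment emergent? | Protocol 10.1.1 | No |
| Is it treatment emergent? | SAP 7.1.2 and 7.6.1 | Yes |
| Is it tabulated? | SAP 7.6.1 | Yes, under all and unrelated TESAEs, if the SAP rule is used |

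The answers differ at two stages, collection and TEAE classification.

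**3. Share of each endpoint window in conflict.** Inputs are the nominal days in Table 2: first dose Day 1, 28 days post boost Day 50, Month 3 Day 85, Month 6 Day 184, Month 12 Day 366. Formula: (D − 50)/(D − 1).
- Month 3: (85 − 50)/(85 − 1) = 35/84 = 41.7%
- Month 6: (184 − 50)/(184 − 1) = 134/183 = 73.2%
- Month 12: (366 − 50)/(366 − 1) = 316/365 = 86.6%

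These are shares of follow-up time, not shares of events lost.

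**4. Illustration by assumption.** Suppose the risk of an SAE after Day 50 is 2%, 5% or 10% per subject, and that 0% to 50% of such SAEs are judged related. Both inputs are assumptions.

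| Assumed risk | Expected subjects with an SAE per 24 | Left per 24 if only related SAEs are kept | Expected among all 144 | Left among all 144 |
|---|---|---|---|---|
| 2% | 24 × 0.02 = 0.48 | 0 to 0.24 | 2.88 | 0 to 1.44 |
| 5% | 24 × 0.05 = 1.2 | 0 to 0.6 | 7.2 | 0 to 3.6 |
| 10% | 24 × 0.10 = 2.4 | 0 to 1.2 | 14.4 | 0 to 7.2 |

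If sites follow 10.2.3 the loss is zero. In a group of 24, each subject with a missed SAE moves the proportion by 1/24 = 4.2 percentage points.

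**The case against.** The strongest reply is that the specific SAE section governs. Section 10.2.2 concerns unsolicited AEs, its sentence is additive (it says also), and the related qualifier could attach to AEs alone. Section 10.2.3 is explicit that causality is irrelevant. Section 10.4, on follow-up, also pairs all SAEs with AEs that have relevance. The 9.3.6 list is evidently abbreviated, since it omits the Visit 11 thyroid test that Table 2 schedules, and 9.3 refers to Table 2 for all trial procedures. The study is a descriptive phase I trial with no formal testing, and the endpoint is secondary.

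Much of this stands, and it rules out several stronger readings that a reader might infer:
- *That the protocol simply restricts late SAE collection to related events.* It does not. 10.2.3 and Table 2 say otherwise, and the synopsis mentions related AEs without excluding anything else.
- *That the SAP tables drop unrelated late SAEs.* They do not under the SAP's own rule, and unrelated TESAEs have their own table.
- *That late enhanced disease or COVID-19 would be lost.* Protocol 10.1.4 requires AESIs to be reported whatever their causality, 10.1.3 treats confirmed COVID-19 during observation as an SAE without a relatedness test, and SAP 7.6.1 tabulates unrelated AESIs.

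The reply does not remove the conflict. The word also extends collection beyond Day 50, but it does not delete the qualifier related, and no order of precedence is given. The protocol and SAP definitions of TEAE differ, and the SAP gives TESAE no separate definition that would settle the matter.

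**Conclusion.** The contradiction is real and of moderate weight. The long-term SAE proportion may depend on causality judgements if 10.2.2 is read narrowly or the protocol's TEAE rule is applied. It need not if 10.2.3 and the SAP rule are followed. The conflict covers 42%, 73% and 87% of the Month 3, 6 and 12 windows, on nominal visit days.

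A reader might infer that the reported long-term SAE rate would fall to near zero. The documents do not support that. They give no SAE rate and no expected share judged related, and the result would require sites to disregard 10.2.3 and Table 2. The number of SAEs lost cannot be computed from the documents.

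The point is still more than a missing detail, because someone applying a stated rule of the protocol could produce a wrong value for a prespecified safety endpoint.

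**What to change.** 1. Reconcile Protocol 10.2.2, the synopsis and the matching sentence in 13.1.4 with 10.2.3 and the endpoint: all SAEs are collected to Month 12 regardless of causality, and after 28 days post boost only non-serious AEs are limited to related ones. Keep the existing exception for AEs leading to withdrawal or discontinuation. AESIs need no change, since 10.1.4 already ignores causality.
2. List AE and SAE recording in Protocol 9.3.6, to match Table 2.
3. Align the TEAE definitions in Protocol 10.1.1 and SAP 7.1.2, or declare the difference in SAP 2.3.
4. State in SAP 7.6.1 that the SAE endpoint is tabulated for all SAEs after the first dose, cumulative to Months 3, 6 and 12. The SAP names no such table at present.

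The cost is wording in a few sections and one SAP table. The visits and the 24-hour SAE reporting route already exist. The collection wording should be settled before subjects pass Day 50, because events not recorded then may not be recoverable.
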